6.5 Safety Analysis

Safety analyses will involve examination of the incidence, severity, and type of treatment-emergent AEs reported, and changes in vital signs and laboratory test results from baseline (Day -1) to specified time points throughout the study.

6.5.1 Adverse Events

Treatment-emergent AEs reported during the study will be coded using the MedDRA dictionary. An AE will be summarized by dose group and the following:

- System organ class and preferred term
- System organ class and severity
- System organ class, preferred term and severity

These summaries will be presented for the following subsets:

- All adverse events
- Drug-related adverse events
- Adverse events resulting in discontinuation of study drug or the study
- Serious adverse events, including deaths
- Adverse events due to infectious and non-infectious regimen-related toxicities

For tables classifying AEs by severity, if a subject has multiple occurrences of an adverse event with the same MedDRA term, the most severe event will be chosen.

A summary and by-subject listing will be provided for any subject who died, experienced SAEs, or experienced AEs resulting in discontinuation of study drug or the study.

6.5.2 Clinical Laboratory Evaluation

Laboratory values outside of the corresponding normal ranges will be identified and reported to the Sponsor.

The incidence of clinically significant abnormal changes in laboratory values compared with baseline (hematology, chemistry, and urinalysis), and the incidence of DLTs will be summarized by dose group (see Section 3.3.2 for the definition of DLT). MTD will have been exceeded if two or more subjects in a dose group experience a DLT. If, in the subsequent DSMB review of the data, no explanation for the serious adverse events other than use of study drug can be determined, the study may be stopped.

Changes from baseline in special studies parameters (which may include, but may not be limited to, LPS, LBP, BPI, soluble CD14, TLR4, membrane CD14, TNF-RI, IL-1, IL-6, IL-8, IL-10, IL-12 p70 and CRP) will be summarized by dose group.

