1.3 BPI and Opebacan (rBPI₂₁)

Recombinant N-terminal fragments of BPI (including rBPI₂₃ and opebacan [rBPI₂₁, NEUPREX[®]]) possessing the LPS-binding and LPS-neutralizing activity of holo-BPI have been developed as potential anti-infective agents by XOMA (US) LLC (Berkeley, CA). These BPI congeners possess potent *in vitro* endotoxin-neutralizing activity towards LPS in complex biologic fluids including plasma, serum and whole human blood (Weiss et al., 1992). N-terminal rBPI fragments have also demonstrated efficacy in multiple models of endotoxemia of rodents, rabbits, and non-human primates (Rogy et al., 1994; Lin et al., 1994a; Jin et al., 1995; Dahlberg et al., 1996; Lin et al., 1996).

The feasibility and safety of delivering rBPI to humans has been demonstrated in phase I trials where it has been well-tolerated, safe, and non-immunogenic (Wiezer et al., 1998). Intravenous infusion of rBPI₂₃ was able to blunt LPS-induced fever, changes in cardiac index, cytokine release (including TNF α) and activation of clotting cascades in human volunteers (von der Mohlen et al., 1995; von der Mohlen, 1995a). A number of phase II

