5.3 Laboratory Tests/Other Evaluations

This study involves various procedures and tests performed repeatedly throughout the study. If a subject has a clinically significant abnormal laboratory test value that is not an expected

result of study drug administration or was not present at baseline, the test will be repeated and the subject will be followed until the test value has returned to the normal range or the Investigator has determined that the abnormality is chronic or stable.

The Investigators are required to evaluate all abnormal laboratory results for their clinical significance. An isolated abnormal laboratory result in the absence of any associated clinical finding may not be considered an AE. An abnormal laboratory result will be considered clinically significant and recorded as an AE when it is part of a clinical abnormality requiring specific medical intervention or follow-up.

A complete physical examination will be performed at prescreening, Day 28, Day 100 and hospital discharge. Vital signs will be recorded at specified time points throughout the study. Vital sign measurements consist of blood pressure, pulse rate, body temperature and body weight.

For women of child-bearing potential, a urine or serum pregnancy test will be performed at screening.

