6.5.3 Vital Signs

For each assessment of vital signs, changes in vital signs from baseline will be summarized. Vital signs (including body weight, heart rate, blood pressure, and temperature) will be summarized by dose group and assessment time.

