Appendix 1 (continued) Footnotes to Study BPSC030 Schedule of Assessments

- Chemistries include sodium, potassium, chloride, bicarbonate, glucose, BUN, creatinine, calcium, phosphorus, magnesium, bilirubin (total, and direct if bilirubin > 2.0 mg/dL), albumin, ALT, AST, LDH, alkaline phosphatase, CPK with MB fraction (not done if a cardiac serology assessment is done), and total protein. Coagulation includes PT, PTT, fibrinogen, D-Dimers (or FDP or FSP). Urinalysis includes chemistry and microscopic.
- Successful engraftment must be confirmed by three consecutive daily measurements of ANC $\geq 500/\mu L$, with the first of the 3 days occurring no later than Day 28.
- The metabolic assessment includes the following: 1) Caloric source documentation, including volume and type for all fluids and nutritional sources, performed on Days –1, 0, 3, 7, 10, 14, 17, 21, 24, 28, 35, 42, and 49 or until the subject is released from the hospital, whichever occurs first; and 2) Intake and output (I&O) and total days of parenteral nutrition (TPN), performed daily from Day –1 through Day 49 or until the subject is released from the hospital, whichever occurs first. At final screening, the subject or legal guardian will be asked to provide the subject's recent dietary history. Metabolic assessments requiring daily totals should be measured by calendar day (i.e., from midnight to midnight) unless otherwise specified by institutional standard practice.
- Vital signs include pulse, blood pressure (systolic/diastolic), respiratory rate, and temperature taken in the morning (i.e., the first waking set of vital signs). On Day -1 only, body weight must be measured predose to calculate the study drug dose and temperature is measured twice: predose (within one hour prior to the start of infusion) and postdose (within four hours after the start of infusion). If a subject experiences an SAE, vital signs must be taken more frequently, per standard institutional practice. Vital signs must be recorded every day from Day -1 through Day 49 or until the subject is released from the hospital, whichever occurs first.
- T_{max} is the highest temperature recorded of all measurements taken during a calendar day (i.e., midnight to midnight). On Day –1 only, T_{max} is measured for two separate periods: predose (within one hour prior to the start of infusion) and postdose (within four hours after the start of infusion).
- ¹⁷ On Day –3, LPS but not LBP will be assessed.

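### The only laboratory summary specified by dose group depends on investigator-judged clinical significance and does not name coagulation, so it adds little to the adverse event tables

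*Supplement*

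**What the plan says.** Section 6.5.2 (Clinical Laboratory Evaluation) commits to summarizing by dose group "The incidence of clinically significant abnormal changes in laboratory values compared with baseline (hematology, chemistry, and urinalysis"). The section also covers DLT incidence and changes from baseline in a list of special-studies markers, but coagulation is not on that list. For other abnormal values it says: "Laboratory values outside of the corresponding normal ranges will be identified and reported to the Sponsor".

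Section 5.3 defines the key term: "An abnormal laboratory result will be considered clinically significant and recorded as an AE when it is part of a clinical abnormality" needing specific intervention or follow-up. The sentence before it reads: "An isolated abnormal laboratory result in the absence of any associated clinical finding may not be considered an AE".

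Section 6.5 says more generally that the safety analysis will look at "changes in vital signs and laboratory test results from baseline (Day -1) to specified time points throughout the study". For vital signs, Section 6.5.3 puts this into practice: "For each assessment of vital signs, changes in vital signs from baseline will be summarized".

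Coagulation is a panel of its own in Section 4.3 and in the Appendix 1 footnotes: "Coagulation includes PT, PTT, fibrinogen, D-Dimers (or FDP or FSP"). Section 5.0, like 6.5.2, lists only hematology, chemistry and urinalysis.

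**The concern.** A laboratory table is most useful when it gives a reading of toxicity that does not depend on the AE forms. Here entry to the table depends on the investigator judging a change clinically significant, and Section 5.3 applies nearly the same test to decide whether the result is an AE. The two sources then mostly count the same events.

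This matters because demonstrating safety is the first objective. The study is open-label with successive dose groups, and Section 5.2 expects many laboratory abnormalities in every transplant recipient. What counts as clinically significant can differ between investigators and can drift as groups are enrolled in turn. DLT status also starts from investigator attribution (Section 3.3.2). The AE, DLT and laboratory tables therefore all pass through unblinded judgement. With six subjects per group, one subject is 1/6 = 17% of the group, so a single missed or differently judged value shows in the comparison.

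**Working it through.** The plan states no figure to reproduce, and the study has no formal testing. The check sets the sections side by side, then counts the coagulation data.

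**1. Overlap with the AE tables.** Section 5.3 uses one condition for both labels: being part of a clinical abnormality that needs intervention or follow-up. A result meeting it is clinically significant and is recorded as an AE, so it can appear in the 6.5.2 laboratory table and in the 6.5.1 AE tables. The laboratory table may show the analyte where the AE is recorded under a diagnosis (Section 5.4.1), but the event has already been counted. An isolated abnormal value may fall outside both.

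**2. What lies outside that table.**
- Section 6.5: changes from baseline will be examined, with no statistic or table named.
- Section 6.5.2: out-of-range values go to the sponsor, with no dose-group summary stated.
- Sections 6.5.2 and 6.5.3: change from baseline is specified for special-studies markers and for vital signs, but 6.5.2 does not specify it for routine tests.

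**3. Coagulation.** Scheduled post-baseline days for the joint chemistry, coagulation and urinalysis row of Appendix 1:

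| Dose groups | Days | Panels per subject |
|---|---|---|
| 1, 2, 3 | 3, 14, 21, 28, 100 | 5 |
| 4 | 7, 14, 21, 28, 100 | 5 |
| 5 | 8, 14, 21, 28, 100 | 5 |

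Planned subjects: 6 × 5 groups = 30 (Section 6.2).
Panels: 5 × 30 = 150.
Measures per panel: PT, PTT, fibrinogen, and D-dimers or a substitute = 4.
Values: 150 × 4 = 600.

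This assumes full attendance, no replacement of subjects, no cohort expansion and no extra panels at a diagnosis of grade 2 or higher aGvHD. Day 100 may be done by phone. If no Day 100 blood were drawn at all, the counts would be 4 × 30 = 120 panels and 120 × 4 = 480 values. Section 6.5.2 names no summary for any of them.

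**The case against.** The strongest reply has four parts.

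*Other sections cover much of this.* Section 5.1 includes abnormal laboratory findings in the AE definition. Section 5.2 lists electrolyte disturbances, renal insufficiency and transaminitis among the events to be collected as AEs. These are graded by CTCAE v3.0 and tabulated by dose group and severity (6.5.1). Section 6.5 is not limited to three panels, and Section 4.3 counts coagulation among routine laboratory analyses. This stands. A reader might infer that laboratory toxicity would go unseen or that the plan ignores laboratory change; the documents do not support either.

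*The wording of 5.3 is not absolute.* It says when a result is clinically significant, not only when, and it says an isolated result may not be an AE. This also stands. A reader might infer that the laboratory table can never show anything beyond the AE tables. The text supports a large overlap, not complete identity.

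*There is no coagulation harm signal.* Section 1.3 describes rBPI23 as dampening LPS-induced responses, among them "activation of clotting cascades in human volunteers", and presents this as activity. The heparin restriction comes without a stated reason. Neither shows harm. Coagulation belongs in the tables because it is collected as a safety panel, not because the documents report a risk.

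*Table layouts belong in a SAP.* None is shown, and detailed tables could be set there. This limits the weight of the point. But 6.5.2 is not silent: it states what will be tabulated and for which panels, and a SAP written to follow it would inherit both limits. DSMB review of all available safety information (Section 3.3.4) protects escalation decisions, but it does not set the final summaries.

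**Conclusion.** The point holds for the table specified in 6.5.2, not for the safety plan as a whole. That table largely repeats the AE data through investigator judgement, and the general promise in 6.5 is not carried out for routine tests. Coagulation, at 120 to 150 scheduled post-baseline panels under the attendance assumptions above, has no named summary. How many isolated severe values would be missed cannot be estimated from the documents. The conclusion rests on reading 5.3 as tying clinical significance closely to AE recording, and on no unseen SAP already supplying these tables. The change is worth making but is not critical: the data will exist, and the gap is in how they are summarized.

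**What to change.** In Section 6.5.2, add by dose group:

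- shift tables from Day -1 grade to worst post-baseline CTCAE v3.0 grade, computed from the laboratory values without investigator judgement, for chemistry, coagulation and hematology;
- normal-range shifts for any analyte without a grade;
- changes from baseline by scheduled day for the same panels, as 6.5.3 already does for vital signs. The first post-baseline chemistry and coagulation draw is on Day 3, 7 or 8 depending on the group, so the groups line up directly only from Day 14.

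State whether unscheduled values count towards the worst grade. Add coagulation to the panel lists in Sections 5.0 and 6.5.2. Keep the investigator-judged incidence as a supplement.

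The cost is modest programming on data already collected, with no added visits or tests. Hematology shifts will discriminate little between groups, because Section 1.4 puts the ANC near zero in the first weeks after transplant; the gain lies mainly in chemistry and coagulation. Starting from the Day -1 grade allows for abnormalities already present after conditioning.

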6.5.3 Vital Signs

For each assessment of vital signs, changes in vital signs from baseline will be summarized. Vital signs (including body weight, heart rate, blood pressure, and temperature) will be summarized by dose group and assessment time.

6.5.4 Antibody Response to Opebacan

The proportion of subjects with an antibody response to opebacan will be summarized by dose group.

6.5.5 Concomitant Medication

Concomitant medications will be classified according to ATC codes in the World Health Organization Drug (WHODRUG) dictionary. The number and percent of subjects using each class of concomitant medication will be tabulated by dose group. The table will be sorted alphabetically.

6.6 Missing Data

Safety results will be summarized using all available data. Multiple attempts will be made to obtain missing data. Missing data will not be imputed.

6.7 Pharmacokinetic, Pharmacodynamic, and Other Analyses

Non-compartmental pharmacokinetic analysis will be performed on the data. The following pharmacokinetic parameters will be obtained: peak concentration after the 30 minute dose, steady state concentration during long-term infusion, endogenous BPI levels measured at predose and 24 hours after the end of the last infusion, and opebacan clearance.

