3.2.1.3 Endogenous BPI and LPS Levels Following Hematopoietic Stem Cell Transplant

Levy, [name] and colleagues, and XOMA are presently conducting a study to investigate the endogenous background levels of BPI and LPS in patients undergoing HSCT. Recent human data have shown that, post-conditioning, patient blood levels of endogenous BPI drop to undetectable levels rapidly as the ANC falls. During this period there is a concomitant rise in LBP (indicating endotoxemia); furthermore, as neutrophils recover in these patients, circulating levels of BPI rise and LBP diminish to normal pre-inflammatory levels (Levy, [name], et al., unpublished observations, Figure 2).

Figure 2
Plasma Concentrations in Patients Undergoing HSCT

Based on all of the above, it is hypothesized that continuous administration of opebacan therapy to provide continuous drug levels, before infusion of donor cells, will make BPI available to neutralize circulating endotoxin and ameliorate endotoxin-mediated activation of the innate immune system, thus preventing or reducing complications associated with endotoxemia, including aGvHD.

3.2.1.4 Nonclinical Safety Assessment Summary

The general toxicity of opebacan was assessed in the rat and the monkey using the IV route of administration (bolus administration, continuous and intermittent infusion) for up to 28 days. Doses evaluated in these studies ranged from 2 to 200 mg/kg/day in the rat and from 10 to 200 mg/kg/day in the monkey.

[figure not shown]
Dose-related myocardial toxicity was observed in a single rat and a single monkey study following continuous infusion of formulated opebacan at ≥ 100 mg/kg/day for 3 to 5 days. No cardiotoxicity was seen in a number of other studies where formulated opebacan was continuously administered at doses up to 120 mg/kg/day in the rat and up to 75 mg/kg/day in the monkey for the same or longer duration, and where formulated opebacan was administered intermittently 4 times a day for 28 days at doses up to 150 mg/kg/day in the rat and up to 100 mg/kg/day in the monkey. The later data suggests that the duration of exposure may pose a greater risk of cardiac toxicity than the total daily dose.

Steady-state plasma opebacan levels were calculated for the rat and monkey studies where cardiotoxicity was evident. In the rat study, the steady-state plasma opebacan level corresponding to the cardiotoxic dose was approximately 3 µg/mL, and the no-observed-

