3.3 Selection of Doses Used in the Study

3.3.1 Dosing Groups

Eligible subjects in five successive dose groups of six subjects each will be treated with opebacan at the dose levels and dose durations shown in Table 1. All subjects will receive a 4 mg/kg continuous IV infusion for 30 minutes. Subjects enrolled in Dose Groups 1, 2, and 3 will then receive a continuous IV infusion at 6 (Group 1), 9 (Group 2) or 12 mg/kg/day (Group 3) for 3 days. For subjects in Dose Groups 4 and 5, the original rapid infusion will be followed, by a continuous IV infusion at 12 mg/kg/day for 7 (Group 4) or 14 (Group 5) days.

Subjects whose conditioning regimen includes total body irradiation (TBI) will have three 1-hour interruptions in their opebacan infusions (one on Day –1 and two on Day 0) to accommodate TBI treatment. Following the final interruption on Day 0, the infusion must be restarted at least 2 hours prior to the HSCT.

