3.9 Assay Methods

3.9.1 Pharmacokinetics Assay

A sandwich ELISA was developed for the measurement of opebacan in plasma. The ELISA utilizes an affinity-purified rabbit anti-BPI antibody for solid-phase capture and a biotin-labeled rabbit anti-BPI antibody (followed by streptavidin-alkaline phosphatase) as the detector. A standard curve is plotted as A_{405} versus concentration. A four-parameter fit is performed and concentrations are determined for samples and controls by interpolation from the standard curve.

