- ⁸ DNA testing includes SNPs for markers such as TLR and TNF at select sites only. DNA samples obtained from consenting donors will be taken at the time of stem cell harvest.
- ⁹ The "Signs and Symptoms Inventory" CRF page must be completed on Day –1 prior to dosing.
- See Appendix 2 for a table showing the multiple PK sample collection time points on Days –1, 2, 6 and 13 not captured in this table. For Dose Groups 1, 2, and 3, multiple PK time points occur on Days –1 and 2. For Dose Group 4, multiple PK time points occur on Days –1 and 6. For Dose Group 5, multiple PK time points occur on Days –1 and 13. Note: PK sample must be drawn from a different vein than that used for opebacan administration.
- The PK samples for the donor and subject at prescreen and for the subject at predose on Day –1 are used for measuring the level of endogenous BPI.

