 - Donors collected at a single time-point
 - Patients collected
 - Baseline
 - Day 0, +7, +14, +21, +28
 - At the time of diagnosis of aGVHD
- Preliminary correlation with characteristics and outcome

[figure not shown]
Results

[figure not shown]
- 30 recipient:donor sibling pairs
- 18 M:12 F
- 17 adult pairs (median age R:D 39:43)
- 13 pediatric pairs (median age R:D 14:11)
- ALL 8, AML 8, CML 4, MDS 4, HD 2, AA 2, CLL 1, NHL 1
- TBI=25 (83%), BU=3 (10%), CTX=30 (100%)

Prolonged neutropenia in patients undergoing HSCT

[figure not shown]

Lower Plasma BPI/LBP Ratio Associated With AGVHD

Features of patients who develop aGVHD

- Lower plasma BPI at baseline
- Higher plasma LBP at baseline
- Other evidence of LPS-related innate immune activation at baseline and day 0

Consistent with hypothesis:

- LPS \longrightarrow TLR4 \longrightarrow TNF- α \longrightarrow aGVHD
- Addition of BPI may shield against this process

Protocol Objectives

- To demonstrate safety of escalating doses of opebacan in myeloablative allogeneic HSCT
- To determine pharmacokinetics of opebacan in myeloablative allogeneic HSCT
- To determine if IV opebacan is associated with changes in biological markers for inflammation
- To develop preliminary descriptive data on the occurrence and severity of HSCT-related complications, including acute GvHD

Study Design

- Phase I/II, open-label, dose-escalation study of the safety and PK of opebacan in subjects undergoing non-T cell depleted myeloablative allogeneic HSCT
- Subjects who sign informed consent and pass initial screening prior to HSCT conditioning will be re-evaluated at Day –1 following completion of conditioning
- Those subjects who meet eligibility criteria at final screening will receive opebacan by continuous IV infusion beginning on Day –1
- Eligible subjects will be assigned to one of five successive dose groups of six subjects each. Each dose group must contain at least two pediatric subjects and two adult subjects.

Pre-Screen Inclusion Criteria

- Subject and/or legal guardian have signed consent
 IV catheter maintained in subject for the purpose of opebacan administration
- Age ≤ 60 and undergoing allogeneic myeloablative HSCT
- Life expectancy ≥ 8 weeks
- Scheduled for treatment with a myeloablative conditioning regimen
- Meets standard performance and end-organ function criteria for HSCT
- Female subjects of child-bearing age negative urine pregnancy test

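### Section 6.7 reports the sample taken 24 hours after infusion as endogenous BPI, but the assay described is not shown to separate native BPI from opebacan

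*Supplement*

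**What the plan says.** Section 6.7 lists the non-compartmental PK parameters: the peak after the 30-minute dose, the steady-state level during the long infusion, opebacan clearance, and "endogenous BPI levels measured at predose and 24 hours after the end of the last infusion".

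Section 3.9.1 describes one PK assay: "A sandwich ELISA was developed for the measurement of opebacan in plasma". It "utilizes an affinity-purified rabbit anti-BPI antibody for solid-phase capture and a biotin-labeled rabbit anti-BPI antibody". The section does not say whether the assay tells opebacan from native BPI, and it gives no limit of quantification.

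Appendix 1, footnote 11, says that the donor and subject PK samples at prescreen and the sample "for the subject at predose on Day –1 are used for measuring the level of endogenous BPI". Appendix 2, footnote 3, says the same. Neither mentions the sample 24 hours after the end of infusion. Section 3.8.3 lists that draw (Day 3 in Groups 1–3, Day 7 in Group 4, Day 14 in Group 5) among the samples for the pharmacokinetics of opebacan.

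On the native level to expect, Section 3.2.1.3 says that after conditioning "patient blood levels of endogenous BPI drop to undetectable levels rapidly as the ANC falls", and that BPI rises again as neutrophils recover.

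**The concern.** One blood sample carries two roles. In the schedule it belongs to the drug's post-infusion profile; in the analysis section it is a measure of the patient's own BPI. Opebacan is a recombinant fragment of BPI (Section 1.1), and the plan already relies on the PK samples to read native BPI before dosing. Unless the assay is shown to be specific, a post-dose reading is the sum of drug and native protein.

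Where native BPI is near zero, even a small drug residue could make up much of the reading. A residue that scales with dose would then look like a dose-related rise in endogenous BPI. Section 6.5.2 also plans to summarise change from baseline in BPI by dose group, so the label could carry into that table.

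**Working it through.** **1. The passages side by side**

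| Place | Samples tied to endogenous BPI |
|---|---|
| Section 6.7 | Predose; 24 h after end of infusion |
| Appendix 1, footnote 11 | Prescreen; Day −1 predose |
| Appendix 2, footnote 3 | Prescreen; Day −1 predose |
| Section 3.8.3 | Prescreen (the +24 h draw is listed as an opebacan PK sample) |

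The conflict over the +24 h sample is textual and needs no kinetic assumption.

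**2. The plan's expected level, reproduced.** Section 3.2.1.4 says that 24 mg/kg/day should approach 1 µg/mL.
- Clearance = rate ÷ level = 24,000 µg/kg/day ÷ 1 µg/mL = 24,000 mL/kg/day, or 24,000 ÷ 24 = 1,000 mL/h/kg (1 L/h/kg).
- Level at 12 mg/kg/day = 12,000 ÷ 24,000 = 0.5 µg/mL. This matches the plan's figure of about 0.5 µg/mL.
- Doubling the 250–280 ng/mL quoted for 6 mg/kg/day gives 500–560 ng/mL, which agrees.

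**3. Drug left 24 hours after the end of infusion.** The documents give no half-life, so it is an assumption here. With one-compartment decay, residue = steady-state level × 2^(−24/half-life).

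| Assumed half-life | From 500 ng/mL (12 mg/kg/day) | From 250 ng/mL (6 mg/kg/day) |
|---|---|---|
| 1 h | below 0.001 | below 0.001 |
| 2 h | 0.12 | 0.06 |
| 4 h | 7.8 | 3.9 |
| 6 h | 31 | 16 |

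(ng/mL)

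The residue exceeds 1 ng/mL, a reference value chosen only for illustration, when the half-life is above 24 × ln 2 ÷ ln 500 = 2.7 h. From 250 ng/mL the threshold is 24 × ln 2 ÷ ln 250 = 3.0 h.

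**4. Which end of the range is likelier.** In the same model, volume = clearance × half-life ÷ ln 2. At 1 L/h/kg, half-lives of 2, 4 and 6 h need volumes of 2.9, 5.8 and 8.7 L/kg. The high implied clearance therefore points to a short half-life, though it does not settle the matter because no volume is given. If decay has a fast and a slow phase, the slow phase starts below the steady-state level, so the table overstates the residue for a given terminal half-life.

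**5. Samples available for steady state.** Subjects on total body irradiation (TBI) regimens "will have three 1-hour interruptions in their opebacan infusions", the last on Day 0. HSCT is at most 36 h after the start of infusion and the restart at least 2 h before it, so the last restart is at most 36 − 2 = 34 h. The earliest 48 h draw is 48 − 1 = 47 h, which is 47 − 34 = 13 h later. The end-of-infusion sample, and Days 6 and 10 in Group 5, are later still.

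**The case against.** The parameter is descriptive: no formal testing is planned, and the trial's hypothesis concerns the effect of infused opebacan, not native BPI after the drug stops. The footnotes say what the prescreen and predose samples are for; they do not say that no other sample may serve. With the short half-life suggested by step 4, the residue could be too small to matter. All of this stands, and it limits the weight of the point. It does not supply the missing statement that the assay can tell drug from native protein.

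Two stronger readings are tempting, and the documents do not support them.

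- *A reader might infer that whatever is measured at +24 h is mainly leftover drug.* Without a half-life or an assay limit this cannot be shown. In Group 5 the sample falls on Day 14. Section 1.5 puts neutrophil recovery at one to several weeks, so part of the reading there could be genuine native BPI.
- *A reader might infer that the Day 0 sample, which can fall in or soon after a TBI stop, lowers the steady-state level and inflates clearance.* The nominal 24 h draw can coincide with a stop or restart when HSCT is at 26 h or later. But Section 6.7 never calls it a steady-state sample, and every group has later on-infusion samples clear of the interruptions. What is missing is only the name of the samples to be used.

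**Conclusion.** The point holds as a fault of specification. Section 6.7 names as endogenous BPI a value that the described assay is not shown to isolate, at a time that the schedule footnotes do not assign to it. A measurable level at +24 h cannot be attributed to endogenous BPI, in whole or in known part.

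The size of any drug contribution is open: negligible for half-lives up to about 2 h, and 7.8 to 31 ng/mL for 4 to 6 h, from a 500 ng/mL steady state. These figures rest on assumed half-lives and one-compartment decay. The labelling conflict rests on neither.

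The steady-state question is a minor clarification and not a demonstrated bias.

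**What to change.** In Section 6.7:

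1. Take endogenous BPI from prescreen and Day −1 predose, plus the Day 100 PK sample already drawn. Bring the footnotes to Appendices 1 and 2 into line.
2. Report the sample 24 hours after the end of infusion as total BPI (opebacan plus endogenous), within the post-infusion concentration profile. Use the same label for any post-dose BPI value in the Section 6.5.2 summary.
3. Do not subtract predose BPI when deriving clearance. The protocol expects native BPI to fall to undetectable levels, so a fixed subtraction would remove a component no longer present, understate the drug level and overstate clearance.
4. Minor: state that steady state is taken from the on-infusion samples at 48 h and end of infusion, with Days 6 and 10 added in Group 5.

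The cost is wording only, with no added visit, blood draw or assay. If the sponsor holds data showing that the ELISA separates the two proteins, saying so in Section 3.9.1 would be an alternative to item 2.
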